¹Pre-study assessments need to be completed within 14 days prior to randomization. Day 1 must occur within 5 calendar days of randomization.

²Subjects who discontinue during the On-therapy Period in the absence of progressive disease will enter the Off-therapy Observation Period of the study (see schedule below). If at any time a subject initiates a non-protocol therapy, the subject will be removed from study and treated as per individual investigator discretion.

³In addition to the end of each month visit assessments. Window for all visits is during treatment is ± 2 days. Window for laboratory assessments before study visits is -7 days.

⁴Complete these assessments if a subject develops PSA or radiographic progression before the end of Month 12. The subject will then be removed from study and treated as per individual investigator discretion

⁵Choice of LHRHa is per investigator's discretion. The first dose of ARN-509 or LHRHa will be on Day 1. ARN-509 will be administered daily with or without food. All subjects should be following a 28-day, 28-day, 35-day schedule for their monthly visit (i.e., the 1st post-Day 1 visit is scheduled for 28 days later, the 2nd post-Day 1 visit is scheduled for 28+28 days later, the 3rd post-Day 1 visit is scheduled for 28+28+35 days later, the 4th post-Day 1 visit is scheduled for 28+28+35+28 days later, etc). If a subject does not receive a scheduled LHRHa injection within ± 7 days of the scheduled due date for injection, he will be removed from study

⁶Physical exam changes will not be collected in the eCRF, any change in physical exam from baseline needs to be recorded on the adverse event page

⁷Adverse event collection starts from signing the ICF. For subjects who discontinue therapy and do not proceed to the Off-therapy Period, AEs must be recorded up to 30 days after the last dose of study medication.

⁸See Section 7.5.4.

⁹Scans need to be done within 6 weeks prior to randomization. At the Progression Visit, scans may be omitted if already done within the prior 1 month.

¹⁰At the Progression Visit, may be omitted if already done with the prior 1 month.

¹¹For reference, see, <https://www.shef.ac.uk/FRAX/tool.aspx?country=9>. DEXA scan is also to be used for osteoporosis assessment.

¹²DEXA scan needs to be done within 12 weeks prior to randomization. At Progression Visit, scans may be omitted if already done within the prior 1 month.

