The time to serum testosterone recovery to > 50 ng/dL and > 150 ng/dL after the cessation of protocol therapy at 12 months will be compared for ARN-509 + LHRHa vs. LHRHa monotherapy. The probability distributions by treatment group of the time to testosterone recovery will be estimated using the Kaplan-Meier method. The log-rank test will be used to compare the distribution of time to testosterone recovery. Subjects who discontinue study drug prior to 12 months for disease progression, unacceptable toxicity, or study withdrawal, as well as subjects who continue hormonal therapy after 12 months or receive non-protocol therapy, will not be included in the analysis of this exploratory endpoint.

No adjustment for multiple comparisons will be made for the analysis of the secondary and correlative endpoints. Some correlative analyses may be deferred or not done if, for any reason, the analysis will have no scientific value.

Safety Analysis:

The verbatim terms used in the electronic case report form (eCRF) by investigators to identify adverse events will be coded using the most current version of the Medical Dictionary for Regulatory Activities (MedDRA). Toxicities will be graded for severity according to NCI-CTCAE Version 4.03 (see Section 12.1.5). All reported adverse events with onset during the On-therapy Period up to 30 days after the last dose of study medication will be included in the analysis.

Specifically, the following adverse events will be summarized:

- All adverse events
- Grade 3 or higher adverse events
- Serious adverse events

- Adverse events leading to discontinuation of treatment
- Adverse events leading to death

Summaries, listings, or subject narratives may be provided, as appropriate, for those subjects who died, who discontinue treatment due to an adverse event, or who experience a \geq Grade 3 or higher or a serious adverse event.

In addition, abnormal findings in physical exams and laboratory tests will be summarized.

Biomarker analysis

Biomarker analyses will be conducted on archival FFPE blocks or slides, plasma and whole blood samples collected from subjects who consented to participate in biomarker analysis to assess AR^{F876L} mutation and other resistance markers from all 3 treatment groups.

Further association may be made with clinical endpoints with:

- Markers identified from RNAseq analysis of archival tumor samples

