5.3 Secondary Endpoints

The following secondary endpoints will be analyzed:

A) Quality of Life:

- Mean change from baseline in total FACT-P score over time
- Mean change from baseline in EORTC QLQ-C30/PR25 score over time
- Mean change from baseline in SHIM score over time

B) PSA Modulation:

- Time to PSA progression, which is defined as a rise to greater than 50% of the baseline serum PSA or rise of 2 ng/mL or more above the nadir, whichever is higher, confirmed by repeat measurement at least 2 weeks later (see Table 1 for the censoring rules).
- Proportion of subjects without evidence of PSA or radiographic progression during the 24-month treatment period and with recovery of serum testosterone at 24 months. Testosterone recovery will be defined as a serum testosterone greater than 150 ng/dL.
- Proportion of subjects with a PSA less than 0.2 ng/mL after 7 months of protocol therapy

C) *Metabolic and Hormonal*

- Mean change from baseline in markers of insulin resistance (including body mass index, fasting glucose/insulin, and hemoglobin A1C), fasting lipid profile, and bone mineral density as measured at the femoral neck, and lumbar spine by DEXA scan over time
- Time to testosterone recovery to greater than 50 ng/dL (non-castrate) and greater than 150 ng/dL during the off-therapy observation period for subjects randomized to the LHRHa-based treatment arms (see Table 1 for the censoring rules)
- The mean change from baseline in serum DHT and estradiol levels over time

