5.3.1.3 Metabolic and Hormonal Parameters

The mean change from baseline for markers of insulin resistance (including fasting glucose, insulin, body mass index, and hemoglobin A1C), fasting lipid panel (including total cholesterol, LDL, HDL, and serum triglycerides), and hormone levels (including DHT and estradiol) analyzed using a similar approach as for the primary endpoint.

The mean change in bone mineral density at the femoral neck, and lumbar spine as measured by DEXA scan will be compared for apalutamide monotherapy vs. LHRHa monotherapy and apalutamide + LHRHa vs. LHRHa monotherapy using an analysis of covariance that controls for baseline values of the corresponding measurement.

The time to serum testosterone recovery to > 50 ng/dL and > 150 ng/dL after the cessation of protocol therapy at 12 months will be compared for apalutamide + LHRHa vs. LHRHa monotherapy. The probability distributions by treatment group of the time to testosterone recovery will be estimated using the Kaplan-Meier method. The log-rank test will be used to compare the distribution of time to testosterone recovery. Subjects who discontinue study drug prior to 12 months for disease progression, unacceptable toxicity, or study withdrawal, as well as subjects who continue hormonal therapy after 12 months or receive non-protocol therapy, will not be included in the analysis of this exploratory endpoint.

No adjustment for multiple comparisons will be made for the analysis of the secondary and correlative endpoints.

Table 1: Key censoring rules

Scenario	Censoring rule
Time to PSA Progression	
 Any increase in PSA to $> 50\%$ of the baseline value or an increase of ≥ 2 ng/mL above the nadir, whichever is higher, and confirmed by repeat measurement at least 2 weeks later is considered an event. Subjects who have no PSA progression at the time of analysis will be censored at the last known date of PSA assessment. Subjects without a baseline PSA or without any post baseline values will be censored at randomization date.

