Time to Serum Testosterone Recovery	
 Any testosterone value between 12 months to 24 months that is greater than 150 ng/dL (or 50 ng/dL as the case may be) is considered an event. If a subject had testosterone recovery (between 12 and 24 months) that happened after hormonal or subsequent therapy started, then the subject is censored at the hormonal or subsequent therapy start date. If a subject had testosterone recovery (between 12 and 24 months) that happened before hormonal or subsequent therapy started, then the recovery is considered as an event. Subjects who were not treated will be censored at randomization date. Subjects who do not fall under any of the above-mentioned category will be censored at the end of on-therapy period or off-therapy period (if the subject is in the off-therapy period).

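### Time to testosterone recovery: the text excludes men who receive non-protocol therapy, Table 1 keeps men who start therapy, and Table 1's censoring date for an unrecovered treated man depends on whether recovery is recorded later

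*SAP*

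**What the plan says.** **Who is analysed.** SAP 5.3.1.3 compares time to testosterone above 50 and above 150 ng/dL, after therapy stops at 12 months, between combination therapy and LHRHa alone. It leaves out men who discontinue study drug before 12 months, "as well as subjects who continue hormonal therapy after 12 months or receive non-protocol therapy, will not be included in the analysis". Protocol 11.4.2 carries the same rule: "subjects who continue hormonal therapy after 12 months or receive non-protocol therapy, will not be included in the analysis of this exploratory endpoint".

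**How men are censored.** SAP 5.3 lists the endpoint as recovery "during the off-therapy observation period for subjects randomized to the LHRHa-based treatment arms (see Table 1 for the censoring rules". Table 1 then distinguishes four cases:

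- Recovery recorded after therapy started: "then the subject is censored at the hormonal or subsequent therapy start date".
- Recovery before "hormonal or subsequent therapy started, then the recovery is considered as an event".
- Untreated men: "Subjects who were not treated will be censored at randomization date".
- Everyone else "will be censored at the end of on-therapy period or off-therapy period (if the subject is in the off-therapy period".

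**What counts as non-protocol therapy.** Protocol 3.1 defines it as any restart of hormonal therapy or start of another anti-cancer therapy. Protocol 7.5 and 7.6 and SAP 2.2 and 2.3 apply the term to therapy given without PSA or radiographic progression.

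**What happens on starting it.** Protocol 7.1, footnote 2: "If at any time a subject initiates a non-protocol therapy, the subject will be removed from study". Protocol 3.1 also removes men at progression.

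**Other rules that touch the endpoint.** SAP 2 measures time-to-event endpoints from randomization. SAP 2.1 applies an mITT exclusion (withdrawal before 24 months) to outcomes related to testosterone recovery; only the 24-month proportion in SAP 5.3.1.2 invokes it.

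**The concern.** The section text and its own table give different instructions for the same men. One programmer would drop a man who recovers at Month 15 and starts therapy at Month 18; another would count him as an event. With about 30 men randomized per arm, moving a few men can move a median.

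Two statistical problems lie beneath the drafting conflict. The exclusion conditions on therapy started after the time origin. If men tend to be retreated once testosterone has returned, it preferentially removes early recoverers. In addition, Table 1 censors at therapy start only when a later recovery is on record. Two men treated on the same day without having recovered can therefore get different censoring dates, according to what is seen afterwards.

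Hypothesis 2 in both documents names adequate testosterone recovery among the findings that would support larger trials of the combination. The study is open-label, so the rule should be settled before the data are examined.

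**Working it through.** The documents give no sample size, event count or rate for this endpoint, so there is no stated figure to reproduce.

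**1. The rules side by side, for a man in an LHRHa arm who completes 12 months**

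| Course after Month 12 | SAP 5.3.1.3 and Protocol 11.4.2 | SAP Table 1 |
|---|---|---|
| Recovers, then starts therapy | Excluded if the therapy is non-protocol | Event |
| Starts therapy, recovery recorded later | Excluded if the therapy is non-protocol | Censored at therapy start |
| Starts therapy, no recovery recorded | Excluded if the therapy is non-protocol | Residual row: end of period |

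On the narrow definition the conflict covers men treated without progression. On the Protocol 3.1 wording it covers every retreated man.

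**2. Which therapy row will usually apply.** Men leave the study at progression and at the start of non-protocol therapy. After that the plan asks for efforts to obtain quality-of-life scales, but schedules no testosterone. Recovery after therapy start will seldom be recorded, so the third line of the table is the usual one for men treated before recovering.

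**3. Size of the residual-row problem (all inputs assumed).** Recovery is exponential with median 5 months off therapy, so a = ln 2 / 5 = 0.1386 per month. Therapy starts before recovery with median m months, so b = ln 2 / m. The window is 12 months, and treated men have no later recorded recovery.

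- Share leaving unrecovered = b/(a+b) × (1 − exp(−12(a+b))).
- If these men stay at risk to Month 24, the apparent median t solves a/(a+b) × (1 − exp(−(a+b)t)) = 0.5.

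For m = 12: b = 0.0578, a+b = 0.1964 and a/(a+b) = 0.7059. Then t = −ln(1 − 0.5/0.7059)/0.1964 = 6.27 months.

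| m (months) | Leave unrecovered | Median, row read as Month 24 | Median, censored at therapy start |
|---|---|---|---|
| 120 | 3% | 5.1 | 5.0 |
| 60 | 6% | 5.2 | 5.0 |
| 24 | 15% | 5.5 | 5.0 |
| 12 | 27% | 6.3 | 5.0 |

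Reading the row as the man's own last day also leaves 5.0. A second simulation used medians of 6 and 10 months, with 10% to 40% starting therapy independently of recovery. Under the Month 24 reading, estimated recovery by 12 months off therapy fell from 75.0% to between 72.0% and 62.1% (median 6), and from 56.5% to between 54.0% and 45.7% (median 10).

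**4. Size of the exclusion problem (same 5-month recovery model, simulated)**

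| Assumed retreatment pattern | Share excluded | Apparent median (months) |
|---|---|---|
| Tends to follow recovery | 10%, 16%, 33%, 50% | 5.2, 5.5, 6.4, 8.4 |
| Independent of recovery | 10%, 20%, 33%, 50% | 5.0 throughout |
| Only men treated before recovery dropped | 3%, 6%, 15%, 27% | 4.9, 4.7, 4.3, 3.7 |

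The direction therefore depends on an unknown. The 10% and 16% cases fit the narrow definition; 33% and 50% need the Protocol 3.1 wording. With recovery seen only at 2-monthly visits, the 10% exclusion and censoring at therapy start both give 6 months, so the difference would not show in the median.

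**5. Between-arm comparison.** With 27 or 20 men per arm, no true difference and retreatment following recovery, simulated log-rank rejection at nominal 5% was 5–6% when exclusion was equal, 5.5–5.6% at 16% versus 10%, and 15–19% only at 50% versus 10%. With the residual row read as Month 24, it was 7–9% when 15% versus 3% left unrecovered and 13–17% at 27% versus 3%. Censoring at therapy start gave 4.5–6.2%. Monte Carlo error is about 0.35 points at 5%.

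**The case against.** **The rules can be applied in sequence.** The text defines the population and Table 1 handles those who remain. On the narrow definition, one would first drop men treated without progression and then use Table 1's therapy rows for men treated after progression. This is a possible reading, and it shrinks the conflict. The SAP never states it, however, and Table 1's rows carry no such limit. Table 1 also has rows for untreated men and for an end of the On-therapy Period, which suggests that it was drafted for a wider set than the text allows. The sequential reading still selects men on a post-origin event.

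**The residual row may already mean the man's own exit.** Its wording is subject-specific, and the off-therapy schedule in Protocol 7.2 includes testosterone at the Progression Visit, so status is measured when a man leaves at progression. On that reading little bias remains. The row does not say so, and a Month 24 date is equally programmable.

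**Stronger readings that a reader might infer.** One is that Table 1 gives no censoring date for men treated before recovering. It does: therapy start, when recovery is recorded later. The gap is confined to treated men with no later recorded recovery. Another is that the medians or the arm comparison will be badly distorted. That needs the broad Protocol 3.1 wording, which follows text on the Follow-up Period and is not repeated in the SAP, or the Month 24 reading. A distorted comparison also needs these losses to differ markedly by arm, which nothing in the documents suggests.

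**The endpoint is exploratory, and SAP 5.1.2 allows sensitivity analyses with censoring rules.** Both are true, and both lower the severity. An optional sensitivity analysis does not settle which rule is primary.

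**Conclusion.** Wrong as written, low severity. The text and Table 1 conflict over men who start therapy after Month 12; the text selects on a post-origin event, and Table 1's censoring date depends on a later outcome. These conclusions rest on the wording alone.

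The size rests wholly on assumed rates. On the narrow definition the exclusion probably moves the median by a few tenths of a month, and possibly not visibly with 2-monthly sampling. The residual row matters only if it is read as Month 24. The arm comparison is biased by the exclusion only if retreatment is related to recovery time and also differs by arm.

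The randomization-date row for untreated men does not suit an origin at the end of therapy, but those men add no risk time, so no estimate changes. The randomization origin in SAP 2 is in practice displaced by the specific wording in SAP 5.3 and 5.3.1.3, though not expressly. The primary FACT-P analysis is not affected.

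**What to change.** State one rule set for this endpoint in SAP 5.3.1.3 and Table 1, and align Protocol 11.4.2:

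- **Population:** men in the two LHRHa arms who complete 12 months of protocol therapy and enter the Off-therapy Period. Men who continue hormonal therapy at Month 12 do not enter it and stay out. Remove the exclusion for therapy started after that point.
- **Origin:** the end of the On-therapy Period, stated as overriding the general definition in SAP 2.
- **Event:** first testosterone above the threshold before any hormonal or subsequent therapy.
- **Censoring otherwise:** the earlier of therapy start and last testosterone sample, replacing Table 1's residual row for this endpoint.
- **mITT:** limit the SAP 2.1 exclusion to the 24-month proportion in SAP 5.3.1.2.
- **Reporting:** by arm, the number of men who started therapy before and after recovery.

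The two wordings of non-protocol therapy should also be reconciled, although this rule set does not depend on which one prevails.

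The cost is minor rewording and programming. No new data are needed: testosterone is already sampled every 2 months off therapy, and Table 1 already relies on the therapy start date. The one downside is the assumption that censoring at therapy start is non-informative. It should be stated, and the counts by arm let a reader judge it.

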5.3.2 Other Evaluations

A) Safety:

- Incidence and severity of adverse events.
- Abnormal findings in physical exams and laboratory tests

B) Correlative Studies

- Frequency of subjects emerging with AR^{F876L} mutation at the end of treatment and progression.
- Frequency of subjects expressing various RNA markers previously demonstrated to confer resistance apalutamide at baseline, end of treatment, and progression

5.4 QOL Scales

5.4.1 FACT-P

The FACT-P scale [version 4.0] is a well validated metric [7] developed by Cella and colleagues, which includes a 27-item “core” quality of life measure (FACT-G) grouped into 4 subscales: physical well-being, social/family well-being, emotional well-being, and functional well-being. There are an additional 12 items specific to prostate cancer; 10 of which are prostate cancer specific physical problems. Items are rated on a 5-item Likert scale, from 0, “not at all”, to 4, “very much” (see Section 11.1). The total range of scores is from 0 – 156. Higher scores indicate higher degree of functioning and better quality of life. Concurrent validity was confirmed by the ability to discriminate subjects by disease stage, performance status, and baseline prostate-specific antigen (PSA) level. Prior clinical trials have established that minimally important differences that are clinically significant and may impact treatment decisions range from 5 to 8 points depending on tumor subtype [8].

5.4.2 EORTC QLQ-C30

The EORTC QLQ-C30 [Version 3] is a well validated [9], and widely used measure of health-related quality of life among cancer patients. The EORTC QLQ-C30 consists of 30 items, which list the functioning and symptoms of cancer patients. Five multi-item function scales are scored: physical function (PF), role function (RF), emotional function (EF), social function (SF), and global health status/quality of life. Furthermore, nine single-item scales (symptoms) are scored, including fatigue, pain, dyspnea, and gastrointestinal problems. The scales are, according to the EORTC guidelines, linearly transformed: all scales range from 0 to 100, in which a higher scale score represents a higher level of functioning. With respect to the single-item scale, a higher score indicates more symptoms or problems; scores of these items will be inverted for the purposes of statistical analysis. In addition, a subscale related to prostate cancer (EORTC QLQ-PR25) will also be administered, consisting of 25 items, with the same linear transformation to a scale ranging from 0 to 100 (see Section 11.2).

5.4.3 Sexual Health Inventory for Men (SHIM)

The Sexual Health Inventory for Men (SHIM) is a well validated [10] abridged 5-item of the 15-item International Index of Erectile Function, which has been extensively studied in men with erectile dysfunction due to various etiologies, including prostate cancer-related therapies. It consists of 5 items pertaining to sexual functioning, with scores ranging from 0-5 for most items. Higher scores indicate higher level of sexual function and less erectile dysfunction (see Section 11.3).

6. SAFETY

6.1 Adverse Events

The verbatim terms used in the electronic case report form (eCRF) by investigators to identify adverse events will be coded using the most current version of the Medical Dictionary for Regulatory Activities (MedDRA). Toxicities will be graded for severity according to NCI-CTCAE Version 4.03. All reported adverse events with onset during the On-therapy Period up to 30 days after the last dose of study medication will be included in the analysis.

Specifically, the following adverse events will be summarized:

- All adverse events
- Grade 3 or higher adverse events
- Serious adverse events
- Adverse events leading to discontinuation of treatment
- Adverse events leading to death

Summaries, listings, or subject narratives may be provided, as appropriate, for those subjects who died, who discontinue treatment due to an adverse event, or who experience a \geq Grade 3 or higher or a serious adverse event.

In addition, abnormal findings in physical exams and laboratory tests will be summarized.

All AEs reported during the AE reporting period (inclusive of the 30-day post last dose of study drug period) will be considered as treatment-emergent adverse events and will be summarized by treatment group as treated using all subjects in the safety population.

For each treatment group, AE incidence rates will be summarized with frequency and percentage by SOC and preferred term, with all subjects treated in that treatment group as the denominator, unless otherwise specified. In addition, AE incidence rates will also be summarized by severity and relationship to study drug. Treatment-related AEs are those judged by the Investigator to be at least possibly related to the blinded study drug. Subjects with multiple occurrences of events will only be counted once at the maximum severity to study drug for each preferred term, SOC, and overall. Deaths that occur within 30 days after the last dose of study drug are defined as on-study deaths.

AE onset date will not be imputed if it's completely missing. Partial AE onset date will be imputed as follows:

- If the AE onset date is missing day only, it will be set to:
 - the first day of the month that the AE occurred, if the month/year of the onset of AE is different from the month/year of the study treatment start.

-
- the day of the study treatment start, if the month/year of the onset of AE is the same as month/year of the study treatment start but different from the month/year of the AE resolution date.
 - the day of the study treatment start or the day of AE resolution date, whichever is earlier if the month/year of the onset of AE and month/year of the study treatment start and month/year of the AE resolution date are same.
 - If the AE onset date is missing both day and month, it will be set to the earliest of:
 - January 1 of the year of onset, as long as this date is after the study treatment start
 - the day and month of the study treatment start, if this date is the same year as that the AE occurred.
 - the AE resolution date.

Summary tables of the following AEs will be provided:

- Overall summary of AEs: the number and percentage of subjects who experienced any AE, any serious adverse event (SAE), any treatment-related AE, any treatment-related SAE, any discontinuations due to an AE, and any deaths
- All AEs by SOC and preferred term All AEs by SOC, preferred term, and toxicity grade
- Grades 3 or 4 AEs by SOC and preferred term
- Treatment-related AEs by SOC and preferred term
- Treatment-related AEs by SOC, preferred term, and toxicity grade
- Treatment-related Grades 3 or 4 AEs by SOC and preferred term
- AEs that led to study drug discontinuation by SOC and preferred term. Study drug discontinuation will be determined from the treatment disposition CRF (where reason for discontinuation is “Adverse Event”) and the specific AE will be determined from the AE CRF page (where action taken is “Drug withdrawn”)
- AEs that led to study drug discontinuation by SOC, preferred term, and toxicity grade
- AEs that led to dose modification by SOC, preferred term, and toxicity grade
- All SAEs by SOC and preferred term
- All SAEs by SOC, preferred term, and toxicity grade
- Deaths will be summarized by time period (on-study vs. during follow-up) and cause of death.

Subject listings of all AEs by toxicity grade, Grades 3 or 4 AEs, all SAEs, AEs that led to study drug discontinuation, dose modification, and all deaths will be provided as well.

Narratives will be written for the following subjects in the final clinical study report:

- Subjects who die ≤ 30 days after the last dose of study drug
- Subjects who discontinue study drug due to treatment-emergent AE

- Subjects who experience a treatment-emergent SAE
- Subjects who experience seizure,
- Subjects who experience other Grade 3 or higher treatment-emergent adverse events of special interest

